## 8. TREATMENT OF SUBJECTS

### 8.1. Description of Study Drug

#### 8.1.1. Investigational Product

Mavrilimumab (KPL-301, formerly known as CAM-3001) is a recombinant human monoclonal IgG4 antibody, which modulates activity of granulocyte-macrophage colony-stimulating factor (GM-CSF) by binding to the alpha subunit of its receptor (GM-CSFR $\alpha$ ).

#### 8.1.2. Description

Mavrilimumab is a sterile, clear to opalescent, colorless to slightly brown-yellow liquid, free from visible particles and is formulated [REDACTED]

[REDACTED] It is supplied by Kiniksa Pharmaceuticals as a liquid in accessorized pre-filled syringes or in vials for parenteral administration. Please see the Pharmacy Manual for additional details.

Matching placebo containing only product diluent/excipients will be provided as a liquid in accessorized pre-filled syringes or in vials for parenteral administration.

#### 8.1.3. Dose and Administration

Subjects will receive a single IV infusion of either 10 mg/kg or 6 mg/kg mavrilimumab or placebo over approximately 60 minutes. The maximum dose may not exceed 1000 mg, which was approximately the maximum dose administered in the Phase 1 study with IV infusion. Dosing will be based on body weight obtained at Screening. Additional details regarding mavrilimumab dosing are provided in Section 9.5.

At any time during the infusion of study drug, should a moderate reaction occur, the infusion will be stopped and restarted at the Investigator's discretion only after the events have resolved. The infusion rate should be re-started at a rate tolerated by the subject. Infusions must be completed within 4 hours of study drug preparation (see Pharmacy Manual for more details).

Use of pre-medication to avoid or treat potential infusion-related reactions is at the discretion of the Investigator. In the event of an infusion reaction, the following interventions can be considered if needed using a separate IV line from that used for the mavrilimumab infusion: NaCl 0.9% IV infusion at 500 mL/hr, diphenhydramine 50 mg IV, hydrocortisone sodium succinate 100 mg IV, epinephrine 1 mg/mL 0.3 mg intramuscular.

### 8.2. Concomitant Medications

No formal drug-drug interaction studies have been conducted with mavrilimumab.

Use of concomitant medications including antipyretics, anti-infectives and anti-fungals, and corticosteroids will be recorded. All investigational and off-label therapies for COVID-19 will be recorded for each subject (eg, chloroquine, hydroxychloroquine, corticosteroids, antivirals [remdesivir, lopinavir/ritonavir]) along with the time, dose, and duration of their administration.

Medication history within 30 days of Screening will be collected.

### 8.2.1. Prohibited Medications

The following medications are also prohibited if use occurred within the timing specified:

- Treatment with cell-depleting biological therapies (eg, anti-CD20) within 12 months prior to Screening,
- Non-cell-depleting biological therapies (such as anti-TNF, anakinra, anti-IL-6 receptor [eg, tocilizumab], or abatacept) within 8 weeks (or 5 half-lives, whichever is longer) prior to Screening,
- Treatment with alkylating agents within 12 weeks prior to Screening,
- Treatment with cyclosporine A, azathioprine, cyclophosphamide, or MMF, or other immunosuppressant therapy (except for corticosteroids) within 4 weeks of Screening.

Medications that become standard of care for COVID-19 and/or receive emergency use authorization may be allowed after discussion with the medical monitor. Use of additional investigational agents using immunosuppressive therapy, as salvage/compassionate use therapy of an alternative agent, may be considered at the discretion of the Investigator in consultation with the Sponsor.

### 8.3. Treatment Compliance

A single IV infusion of mavrilimumab or placebo will be administered over approximately 60 minutes in a clinical setting. No additional procedures for monitoring compliance are necessary.

### 8.4. Randomization and Blinding

#### 8.4.1. Randomization

After meeting all inclusion/exclusion criteria and obtaining informed consent, subjects will be randomized in a 1:1:1 allocation ratio to receive either a 10 mg/kg or 6 mg/kg single IV dose of mavrilimumab, or placebo.

There will be 3 stratification factors for randomization:

1. Use of authorized standard of care antiviral therapy for COVID-19 (eg, remdesivir): yes vs. no
2. Age: < 65 vs.  $\geq$  65 years
3. Acute respiratory distress syndrome (ARDS) status by  $\text{PaO}_2/\text{FiO}_2^*$ : normal-mild ( $> 200$  vs. moderate-severe ( $\leq 200$ ). ARDS status will only be used for Cohort 1 (non-ventilated subjects).

\* If  $\text{PaO}_2$  is unavailable, use  $\text{SpO}_2/\text{FiO}_2$ : normal-mild ( $> 235$ ) vs. moderate-severe ( $\leq 235$ )

An Interactive Web Response System (IWRS) will be used during the study for assignment of a Subject Identification Number at enrollment, randomization to a treatment, and assignment of blinded study drug. A subject is considered randomized into the study when the Investigator confirms the eligibility criteria in the IWRS and the pharmacist has been provided with the investigational product number.

#### **8.4.2. Treatment Blinding**

Subjects, Investigator or designee, and the Sponsor or designee will be blinded to treatment. At the site level, only the clinical site pharmacist will have access to the treatment assignments. The DMC will review the unblinded safety data periodically. If the Investigator decides that unblinding the subject is essential for their clinical management, then the subject may be emergently unblinded, either before or after a discussion between the Sponsor's safety physician or designee and the Principal Investigator. The chair of the DMC will be alerted within 48 hours of any unblinding.

## **9. STUDY DRUG MATERIALS AND MANAGEMENT**

### **9.1. Study Drug**

A single IV infusion of mavrilimumab 10 mg/kg or mavrilimumab 6 mg/kg or matching placebo will be administered to study subjects. Total mavrilimumab dose is not to exceed 1000 mg.

### **9.2. Study Drug Packaging and Labeling**

Each study site will be supplied with study drug in packaging as described in the Pharmacy Manual.

A unique medication number is printed on the study medication label.

### **9.3. Study Drug Storage**

All study treatment must be stored as specified on the label and in the Pharmacy Manual.

### **9.4. Study Drug Preparation**

Individual subject infusions are to be prepared at the investigational site under the authority of the Investigator and in accordance with local regulations. Doses should be prepared for administration via a syringe pump. More detailed instruction will be provided to clinical sites in the Pharmacy Manual (to be developed prior to first Study Initiation Visit).

### **9.5. Administration**

Blinded study drug will be administered as a single IV infusion over approximately 60 minutes by qualified health care personnel. All infusions will be administered in the presence of qualified health care personnel as per local hospital regulations under the supervision of the Investigator or designee. Immediate access to an emergency crash cart will be required. The infusion should last approximately 60 minutes. Premedication to avoid or treat potential infusion-related reaction is at the discretion of the Investigator. The initial 15 minutes of infusion will be administered at an infusion rate to allow for delivery of approximately 1/6 of the total volume of the infusion. If no moderate or severe infusion reactions are observed, the rate will be doubled for the next 15 minutes. After the first 30 minutes the rate will be increased to deliver another 50% of the total volume if the infusion continues to be well tolerated. At any time during the infusion, if a moderate reaction occurs, the infusion will be stopped for a period of at least 30 minutes and restarted at the discretion of the Investigator only after the events have resolved. The infusion should be re-started at a rate tolerated by the subject. The infusion should be stopped permanently if a severe reaction is observed. More detail is provided in Site Manual.

### **9.6. Study Drug Accountability**

The Investigator must maintain an accurate record of the shipment and dispensing of study treatment in a drug accountability log.

## **9.7. Study Drug Handling and Disposal**

Study drug must be received by a designated person at the study site, safely handled and properly stored in a secured location to which only the Investigator and designated site personnel have access. Upon receipt, all study drug must be stored according to the instructions specified on the labels and in the Pharmacy Manual. Clinical supplies are to be dispensed only in accordance with the protocol. Technical complaints are to be reported to the respective Kiniksa Quality Assurance.

At the conclusion of the study, and as appropriate during the course of the study, the Investigator will return all unused study drug, packaging, and drug labels to Kiniksa or their designee.

## 10. ASSESSMENT OF EFFICACY

The following efficacy endpoints will be used for both the Phase 2 and Phase 3 parts of the study. Endpoints will be evaluated for both Cohorts 1 and 2, unless otherwise specified.

### 10.1. Primary Efficacy Endpoint

#### 10.1.1. Cohort 1 (Non-ventilated Subjects)

The primary efficacy endpoint is the proportion of subjects alive and free of mechanical ventilation at Day 29. Mechanical ventilation is defined as invasive mechanical ventilation or ECMO.

Mechanical ventilation status will be evaluated based on the NIAID clinical outcome 8-point ordinal scale. The scale is used to assess clinical status for each day, with the worst score from the previous day recorded. Subjects whose clinical outcome has met an NIAID score of 2 will be considered as using mechanical ventilation.

The NIAID scale is as follows:

- *Death;*
- *Hospitalized, on invasive mechanical ventilation or ECMO;*
- *Hospitalized, on non-invasive ventilation or high flow oxygen devices;*
- *Hospitalized, requiring supplemental oxygen;*
- *Hospitalized, not requiring supplemental oxygen – requiring ongoing medical care (COVID-19 related or otherwise);*
- *Hospitalized, not requiring supplemental oxygen – no longer requires ongoing medical care;*
- *Not hospitalized, limitation on activities and/or requiring home oxygen;*
- *Not hospitalized, no limitations on activities.*

#### 10.1.2. Cohort 2 (Ventilated Subjects)

The primary efficacy endpoint is mortality rate at Day 29, defined as the proportion of subjects who have died by Day 29.

### 10.2. Secondary Efficacy Endpoints

Secondary efficacy endpoints will be examined based on the hierarchical order below.

#### Cohort 1 (Non-ventilated Subjects)

1. Mortality rate at Day 29
2. Ventilation free survival (Time to ventilation or death) by Day 29

Defined as time from randomization to ventilation or death; subjects still alive will be censored at Day 29.

3. Overall survival by Day 29

Defined as time from randomization to death; subjects still alive will be censored at Day 29.

**Cohort 2 (Ventilated Subjects)**

1. Time to 1-point clinical improvement by Day 29

Defined as time from randomization to a 1-point improvement on the NIAID 8-point ordinal scale, or discharge from the hospital, whichever occurs first. Subjects who die before Day 29 will be censored at Day 35.

**10.3. Other Efficacy Endpoints**

[REDACTED]

[REDACTED]

- [REDACTED]
  - [REDACTED]
  - [REDACTED]
  - [REDACTED]
- [REDACTED]
  - [REDACTED]
  - [REDACTED]
  - [REDACTED]
- [REDACTED]

[REDACTED]

- [REDACTED]
- [REDACTED]
  - [REDACTED]
  - [REDACTED]
- [REDACTED]
- [REDACTED]
- [REDACTED]

[REDACTED]

- [REDACTED]
- [REDACTED]
- [REDACTED]
- [REDACTED]
  - [REDACTED]

- 
- A horizontal bar chart titled 'U.S. should take action to address climate change'. The y-axis lists age groups: 18-29, 30-49, 50-69, 70+, and 'All adults'. The x-axis represents the percentage of respondents, ranging from 0 to 100. For each age group, there are two bars: a blue bar for 'Men' and an orange bar for 'Women'. The data shows that in all age groups, a majority of respondents believe the U.S. should take action to address climate change. The percentage of respondents who believe in taking action is generally higher among younger age groups and among women compared to men.
- | Age Group  | Men (%) | Women (%) |
|------------|---------|-----------|
| 18-29      | 88      | 92        |
| 30-49      | 85      | 88        |
| 50-69      | 82      | 85        |
| 70+        | 78      | 82        |
| All adults | 80      | 83        |

#### 10.4. Efficacy Parameters

### 10.4.1. Mechanical Ventilation Parameters

Mechanical ventilation measures for each subject will be recorded daily until the date of Discharge. Ventilation and oxygenation mode and associated measures will be collected. This will include need for high flow oxygen, NIV, IMV, or ECMO and will be recorded daily until the date of Discharge. Effort will be made to collect ventilation supportive measures (eg, pronation, use of nitric oxide, or tracheostomy) received by subjects on mechanical ventilation; further details are provided in the Site Manual.

#### 10.4.2. Respiratory Parameters

Respiratory function parameters will be recorded at the time of randomization for Cohort 1 subjects (abbreviated parameters per the Schedule of Activities) and daily for all subjects until the date of Discharge. At Day 1 the respiratory parameters should be collected at the time closest

to and prior to the initiation of study drug administration. For daily values after Day 1, collect at the time of highest daily  $\text{FiO}_2$ . The collected values will include the peripheral oxygen saturation ( $\text{SpO}_2$ ),  $\text{PaO}_2$  in mmHg (if available) and the amount of oxygen the patient is requiring at the time. If the patient is on mechanical ventilation, noninvasive ventilation (CPAP or BiPAP) or high flow nasal cannula, the oxygen requirement will be the fractional inhalation of oxygen ( $\text{FiO}_2$ ) and will be collected as a percentage. If the patient is on simple nasal cannula, simple face mask or trach collar, the oxygen requirement to be collected is the liter flow expressed as liters per minute (LPM). Other arterial blood gas parameters including pH,  $\text{pCO}_2$ ,  $\text{HCO}_3$ , base excess should be recorded if available. In addition, other supportive measures including pronation, neuromuscular blockade, tracheostomy, ECMO, vasopressor or inotropic therapy, inhaled nitric oxide or others should be recorded.

## 11. ASSESSMENT OF PHARMACOKINETICS

Subjects will provide serum samples for pharmacokinetic studies to be conducted by Kiniksa.

### 11.1. Pharmacokinetic Sampling and Parameter Assessment

Samples will be collected at Screening, Day 1 (prior to the study drug infusion and once it is complete), and at Days 3, 7, 15  $\pm$  2, 29  $\pm$  4, and at the Discharge/UNS visit.

The planned PK parameters for assessment include, but are not limited to, the following:

Parameter	Description
$C_{max}$	The maximum plasma concentration
$T_{max}$	Time of maximum plasma concentration
$AUC_{last}$	Area under the curve from time 0 to time of last measurable plasma concentration, calculated using linear trapezoidal integration
$AUC_{0-\infty}$	Area under the curve from time 0 extrapolated to infinity $AUC_{0-\infty} = AUC_{last} + C_{last}/\lambda_z$ where $C_{last}$ is the last quantifiable concentration
CL	Clearance, $CL = Dose / AUC_{0-\infty}$
$V_z$	Volume of distribution, $V_z = Dose / (\lambda_z \times AUC_{0-\infty})$
$t_{1/2}$	Terminal phase half life, $t_{1/2} = \ln(2)/\lambda_z$
$\lambda_z$	Terminal phase rate constant. Estimated by linear regression of the terminal log-linear phase of the log-transformed concentration vs. time data

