### Schedule of Activities Footnotes

1	Screening activities can occur up to 3 days prior to study drug administration, except for COVID-19 testing (see footnote #4), screening labs (see footnote #17) and chest x-ray or CT scan (see footnote #6). Subject eligibility should be confirmed at Day 1 prior to study drug administration.
2	For hospitalized subjects, this visit will include activities listed. For subjects discharged before Day 15, the Day 15, 22 and 29 visits may be conducted by phone and will not include any laboratory tests, vital signs, or body temperature. For subjects who remain hospitalized after Day 29, the same assessments should be completed on a weekly basis.
3	At the time of discharge, complete ONLY the Date of Discharge / UNS visit assessments on the discharge date (ie, study day assessments are not required). If a subject is discharged and the Investigator judges that it is not safe for the subject to return to the site, or the subject is not willing to return to the site, the required visits (Days 15, 22, 29, 60 and 90) that occur thereafter may be done by phone call follow-up and lab tests will not be performed.
4	Subjects must have a positive SARS-CoV-2 (2019-nCoV) test within 14 days prior to randomization. It does not have to be the first positive test but a positive test is required within 14 days prior to randomization. The test may be performed locally (at the clinical site or from another institution) or by central laboratory if local testing is not available. If SARS-CoV-2 testing is completed post-screening, please enter data into the eCRF.
5	If there is a 1-point worsening in NIAID scale in a subject, it is recommended to re-assess qSOFA (Cohort 1) or SOFA (Cohort 2) at the time of worsening or as per standard of care during hospitalization.
6	Screening x-ray or CT can be done within 7 days from randomization. If performed at additional timepoints by the Investigator/site staff as part of standard of care through Day 29, results will be collected and entered into the eCRF.
7	The discharge X-ray can be done within 72 hours of discharge.
8	Panel includes influenza – A/H3N2, A/H1N1pdm09, A/H7N9, A/H5N1, A, not typed, B, or other (specify); coronavirus – novel CoV, MERS CoV, other CoV (specify); RSV; adenovirus; bacteria; other infectious respiratory diagnosis (specify); clinical pneumonia.

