**Table 4: Schedule of Laboratory Assessments**

Activity / Parameter	Collection Detail	Collection Timepoints
CENTRAL LABORATORY		
Respiratory Panel	A/H3N2, A/H1N1pdm09, A/H7N9, A/H5N1, A, not typed, B, or other (specify); coronavirus – novel CoV, MERS CoV, other CoV (specify); RSV; adenovirus; bacteria; other infectious respiratory diagnosis (specify); clinical pneumonia	Screening
██████████	██████████	████████████████████ ████████████████████ ████████████████████
██████████ ██████████	████████████████████ ████████████████████ ████████████████████ ████████████████████ ████████████████████ ████████████████████	████████████████████ ████████████████████ ████████████████████
Anti-mavrilimumab antibody		Screening and the Discharge/UNS visit
Pharmacokinetic sample		Day 1 (before infusion and when infusion is complete), Days 3±1, 7±1, 15±2, 29+4 and at the Discharge/UNS visit
LOCAL LABORATORY		
Pregnancy test (women of child-bearing potential)	Urine or serum βhCG	Screening and at the Discharge/UNS visit; Day 90+14 is optional
██████████ ██████████		████████████████████ ████████████████████ ████████████████████
Hematology	Complete blood count + differential	Screening (up to 7 days prior to randomization), Days 3±1, 15±2, 29+4 and at the Discharge/UNS visit; Days 60+14 and 90+14 are optional
Coagulation	PT, PTT, and INR	
Chemistry	electrolytes, blood urea nitrogen, glucose and CR	
Liver Profile	AST, ALT, Alb, AlkP, Tbili, Dbili	

Activity / Parameter	Collection Detail	Collection Timepoints
Lipid Panel	Cholesterol, total; high-density lipoprotein (HDL) cholesterol; low-density lipoprotein (LDL) cholesterol (calculation); triglycerides; very low-density lipoprotein (VLDL) cholesterol (calculation)	Screening (up to 7 days prior to randomization) and at the Discharge/UNS visit
Urinalysis		Screening (up to 7 days prior to randomization) and Discharge/UNS visit; Day 29+4, Days 60+14 and 90+14 are optional
Tuberculosis		Optional at Screening - at Investigator's discretion South Africa only: TB testing required for all subjects at Screening
SARS-CoV-2	COVID-19	Screening* Days 1, 2, 3, 4, 5, 6, 7, 8, 15 ±2, 22 ±2, 29 +4 and Discharge/UNS are optional

Screening = up to 3 days prior to randomization

\*For SARS-CoV-2 testing (COVID-19), a positive test within 14 days of randomization is required. Sites that are unable to perform SARS-CoV-2 locally (at the clinical site or from another institution) may use Central Laboratory testing.

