### 12.5.1. Pregnancy Reporting

Formal reproduction toxicology testing of KPL-301 has not yet been performed.

Female subjects of childbearing potential must therefore agree to use a highly effective and protocol-approved contraceptive method (Section 7.1) for the duration of the study (until Day 90), which is 90 days after dosing and covers 5 ½ half-lives of mavrilimumab (approximately 15 days). Regular pregnancy tests will be performed for female subjects of childbearing potential, as defined in the Schedule of Activities (Table 2).

Male subjects who have a female partner of childbearing potential must agree to use a highly effective and protocol approved contraceptive method (Section 7.1) for the duration of the study and until 16 weeks after last study drug administration under this protocol.

If a subject becomes pregnant while participating in the study, study drug dosing must be discontinued immediately.

A female subject must immediately inform the Investigator if she becomes pregnant during the study. A male subject must inform the Investigator if his female partner becomes pregnant during the study. Pregnancies occurring up to 16 weeks after last study drug administration must be reported to the Investigator. The Investigator must report all pregnancies to the Sponsor or designee immediately and no later than 24 hours of their first knowledge of the pregnancy. The Investigator should counsel the subject that it is unknown what effects study drug might have on a fetus. Monitoring of the subject should continue until conclusion of the pregnancy. The newborn should be monitored for a minimum of 6 months after birth, or longer as per local requirement.

Instances of fetal death or congenital abnormality, if brought to the attention of the Investigator at any time after cessation of the study treatment and considered by the Investigator to be possibly related to the study treatment, must be reported to the Sponsor as an SAE.

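### The linear trapezoidal rule for AUClast overstates exposure slightly on the exponential decline: about 1.6% on the full schedule, and up to about 6% if Day 15 is missed but Day 29 is drawn

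*Combined protocol and SAP*

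**What the plan says.** Section 11.1 of the protocol defines AUClast as "Area under the curve from time 0 to time of last measurable plasma concentration, calculated using linear trapezoidal integration". AUC0-inf adds Clast/λz to AUClast, and clearance is dose divided by AUC0-inf. The terminal rate constant λz is "Estimated by linear regression of the terminal log-linear phase of the log-transformed concentration vs. time data". The protocol thus treats the decline as exponential beyond the last sample and as a chain of straight lines before it.

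Table 4 sets the PK draws at "Day 1 (before infusion and when infusion is complete), Days 3±1, 7±1, 15±2, 29+4 and at the Discharge/UNS visit". Section 9.5 says "Blinded study drug will be administered as a single IV infusion over approximately 60 minutes". Section 12.5.1 says that the 90 days after dosing "covers 5 ½ half-lives of mavrilimumab (approximately 15 days". After discharge, footnote 3 to the Schedule of Activities says that visits "may be done by phone call follow-up and lab tests will not be performed".

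Section 13.2.6 says only that PK parameters will be summarised. Both SAPs place PK outside their scope, to be handled separately, so section 11.1 holds the only integration rule in these documents.

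**The concern.** Once the infusion ends, the concentration falls along a convex curve, and a chord between two points on it lies above it. The linear rule therefore adds area on every falling segment, and more on longer ones. The last planned gap, Day 15 to Day 29, is nearly one half-life. It can reach 20 days within the windows (Day 13 to Day 33).

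Any excess in AUClast passes into AUC0-inf, and from there into clearance and volume. Its size depends on which samples a subject provides, so the summaries also carry some avoidable variation between subjects.

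**Working it through.** The documents give no AUC or clearance figure, so there is nothing to reproduce. The check compares the linear rule with the exact area.

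**Inputs.** Half-life 15 days (12.5.1), so λ = ln 2/15 = 0.0462 per day. Nominal times after dosing are 0 (end of infusion), 2, 6, 14 and 28 days (Table 4). Assumptions: one compartment, no assay error, starting concentration 1. Modelling the 60-minute infusion explicitly does not change the rounded full-schedule results.

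**Formula.** On a falling segment of length Δt, with x = λΔt, the relative overstatement is (x/2)·coth(x/2) − 1.

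| Segment (days) | x | Linear area | Exact area | Excess |
|---|---|---|---|---|
| 0–2 | 0.092 | 1.912 | 1.910 | 0.07% |
| 2–6 | 0.185 | 3.339 | 3.330 | 0.28% |
| 6–14 | 0.370 | 5.126 | 5.068 | 1.1% |
| 14–28 | 0.647 | 5.585 | 5.398 | 3.5% |
| Sum | | 15.962 | 15.706 | 1.6% |

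**Full schedule.**
- AUClast: 15.962/15.706 = 1.016, or +1.6%.
- The tail is 0.2742/0.0462 = 5.934, which is 27% of the exact total 1/λ = 21.640.
- AUC0-inf: (15.962 + 5.934)/21.640 = 1.012, or +1.2%.
- Clearance: 1/1.012 − 1 = −1.2%.
- With a half-life of 90/5.5 = 16.4 days, the three figures are +1.4%, +1.0% and −1.0%.

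**Widest last gap (Day 13 to Day 33).** AUClast is 17.27/16.71, or +3.4%. AUC0-inf is +2.6% and clearance −2.5%.

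**Day 15 missed, Day 29 taken.**
- The 6–28 segment is 22 × (0.7579 + 0.2742)/2 = 11.353 against an exact 10.466.
- AUClast: (1.912 + 3.339 + 11.353)/15.706 = 1.057, or +5.7%. AUC0-inf is about +4.1% and clearance −4.0%.
- A Day 10 discharge sample splits that segment into 2.127 + 8.873, and AUClast falls to 16.251/15.706, or +3.5%. A Day 12 discharge sample gives +2.5%.

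**Sampling that stops early** (AUClast against the exact area to the same time).
- After Day 15: 10.377/10.308, or +0.7%.
- Discharge on Day 5, 10, 14 or 20: +0.07%, +0.2%, +0.5% and +0.6%.

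**End-of-infusion sample missed.** The rule then draws a line from zero before dosing to the Day 3 value. With the one-hour infusion modelled, AUClast is −4.6%, AUC0-inf −3.4% and clearance +3.5%.

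**Linear-up/log-down.** The error is 0.0% in every one-compartment case above that keeps the end-of-infusion sample. If that sample is missed, AUClast is −6.2%, which is worse than with the linear rule.

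**Distribution phase** (assumed: half-life 1 to 3 days, 30–50% of the peak, λz from the last three points, full schedule).

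| | Linear | Linear-up/log-down |
|---|---|---|
| AUClast | +2.6% to +3.8% | +0.7% to +1.6% |
| AUC0-inf | +2.4% to −1.6% | +0.7% to −3.6% |
| Clearance | −2.3% to +1.7% | −0.7% to +3.7% |

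The log rule brings AUClast closer to the truth throughout. It does not always do so for AUC0-inf, because the error in λz then also matters.

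**Assay error** (assumed CV 10%). The mean AUClast bias stays at +1.6%, but about 39% of individual values fall below the truth.

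**The case against.** The strongest reply is that the effect is too small to matter. On the full schedule the bias is 1–2%, in parameters that are only summarised. At that size, the choice between linear and linear-up/log-down is one between accepted conventions. This stands as a statement of size, but not as a reason to keep the less accurate rule when the alternative is free.

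A reader might infer that a missed sample always enlarges the bias. The documents point mainly the other way. Samples are lost chiefly through discharge: footnote 2 allows the Day 15, 22 and 29 visits to be by phone for subjects discharged before Day 15, and a PK draw is scheduled at discharge. In those subjects the integration bias shrinks. Their larger problem is that AUClast stops early: for a Day 10 discharge it is 53% below the area to Day 29 (7.36 against 15.70). The integration rule does not cause that and the fix does not cure it. The 5.7% figure needs Day 15 missed, Day 29 drawn and no discharge sample in between. Footnote 3 makes a return for Day 29 possible, but nothing shows how often it happens.

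A reader might also infer a distorted comparison of 6 and 10 mg/kg. No PK comparison of the doses is planned. Under dose-proportional kinetics the percentage bias is the same in both arms for the same sampling pattern, so it cancels in a ratio.

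Finally, a separate PK plan, not among these documents, may already use a logarithmic rule. That is possible, but it would then disagree with section 11.1, which would still need changing.

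**Conclusion.** The point holds as a minor one. With the stated 15-day half-life and one-compartment decline, the rule in section 11.1 overstates AUClast by about 1.6% on the full schedule (AUC0-inf +1.2%, clearance −1.2%). The excess is about 3.5% to 6% when Day 15 is missed and Day 29 taken, and somewhat less if a discharge sample falls nearer Day 15. It is under 1% when sampling ends at discharge or after Day 15.

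The documents do not support saying that exposure is always overstated and clearance always understated. A missed end-of-infusion sample reverses both signs, assay error can reverse the sign in an individual, and with a distribution phase AUC0-inf and clearance can err either way. Errors well above 6% at the stated half-life and planned windows need further missed interior draws or a distribution phase that the documents do not describe.

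No efficacy or safety conclusion depends on these parameters.

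**What to change.** In section 11.1, replace linear trapezoidal integration with linear-up/logarithmic-down trapezoidal integration: linear while concentrations rise, logarithmic while they fall. Carry the same rule into the separate PK analysis plan so that the two agree.

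The cost is a few words and one software setting, with no new samples. The change does not repair a missed end-of-infusion sample or an AUClast cut short by discharge.
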